3.2.4. Tumor Status

Tumor status, as defined by the Response Evaluation Criteria in Solid Tumors (RECIST), will be documented by the treating oncologist.

Tumor status may be classified as: No Evidence of Disease (NED), Progressive Disease (PD), Stable Disease (SD), Partial Response (PR), or Complete Response (CR). For adjuvant stage I, II, & III cancer patients in "remission", prognostic risk factors that predict relapse may also be tracked (based on their stage prognosis). Tumor status will be obtained from the treating oncologist, if deemed appropriate, at each study visit.

Tumor markers (CEA, CA19-9, PSA, CA27-29, CA15-3, CA-125, and/or circulating tumor DNA (ctDNA) or urinary tumor DNA (utDNA) may be drawn at baseline and monthly, according to standard of care and as deemed appropriate/necessary by the treating oncologist.

Tumor status and tumor markers will assist in correlation of viability-sensitivity assays, and correlation of circulating tumor cell enumeration with clinical response.

3.2.5. ECOG Performance Status

The Eastern Cooperative Oncology Group Performance Status (ECOG PS) will be collected at the screening visit as a baseline for all study subjects; during subsequent study visit(s), ECOG may be

Version Date: 8-Dec-2020

Confidential 29 | Page

determined by the treating oncologist and/or Principal Investigator's discretion. Only an ECOG \leq 1 will be considered acceptable for potential leukapheresis collection, whereas for peripheral whole blood collection, capillary blood sampling, discarded tissue and/or fluid collection, as well as other biospecimen collection (i.e., saliva, urine and/or stool), an ECOG \leq 3 will be deemed acceptable.

3.2.6. Concomitant Anticancer Therapy Documentation

Concomitant chemotherapy, biological therapy, hormonal therapy, immunotherapy, or investigational therapy will be allowed during this trial as deemed appropriate standard of care by the treating oncologist. The prior and concomitant anti-cancer therapy regimen will be recorded as part of the study data collection as documented in the Electronic Medical Records (EMR) system at each visit.

3.2.7. Blood Draw for Circulating Tumor Cells and Immune Cells

Using aseptic technique, no more than approximately 100mLs of whole blood from the patient's vein or central access port will be collected for the purpose of this biospecimen collection study during an individual study visit, with no more than approximately 550mLs drawn over an 8-week period. Specialized tubes for maintaining viability of tumor cells and immune cells will be supplied to the site(s) and utilized when deemed appropriate by the principal investigator and/or treating oncologist. In addition, capillary blood draw(s) may occur as needed by experimental design and/or collaborations. Peripheral whole blood draws may be paired with other biospecimen samples, such as tumor tissue, saliva, urine, and stool.

3.2.8. Biopsies

For the purpose of this study, tumor tissue may be collected in cancer patients either through core needle biopsies or surgical resection of the tumor. Core needle biopsies may be performed solely for research purposes by an interventional radiologist under imaging guidance and collected only if there is an acceptably low risk of mortality/serious morbidity. For patients with newly discovered cancers in the pre-surgical or neoadjuvant setting, *BioCytics* may coordinate with the patient's surgeon at the time of their standard medically necessary tumor surgical resection in order to obtain a baseline status of the patient's immune system in their tumor microenvironment, as well as downstream culture applications for both tumor cells and immune cells such as tumor infiltrating lymphocytes (TILs), in addition to furthering genomic and proteomic technologies and antitumor lymphocyte cytotoxicity assays.

3.2.9. Leukapheresis Collection for Circulating Tumor Cells, Immune Cells and Progenitor Cells The intent of leukapheresis in both cancer patients and adult healthy volunteers for the purpose of this study is vast (as referenced in sections 1.3, 1.4, 1.5, and 1.12). Among the most noteworthy is the collection of CTCs including CD133+ cells, collection of immune cell fractions, possible collection of hematopoietic stem and progenitor cells without mobilization, and lastly collection of PBMCs and plasma for prophylactic and therapeutic development against SARS-CoV-2. As a result, cancer patients who are not actively participating in therapeutic experimental clinical trials

Version Date: 8-Dec-2020

Confidential 30 | Page

and adult healthy volunteers who are eligible for leukapheresis collection, study collection visits for leukapheresis will occur no more frequently than every 4 weeks. Leukapheresis will be performed on the Terumo BCT Spectra Optia® or other FDA approved apheresis devices. The collection will be performed based on the study site(s)' approved leukapheresis SOPs when clinical and laboratory safety parameters are met on collection day.

The collection duration may vary depending on the subject cohort and intent of collection; however, most collections will take approximately 1.5 to 2 hours, as long as the safety of the patient is maintained, with an ideal collection time of 1 total blood volume (TBV) processed. Continuous mononuclear cell collection (CMNC) or mononuclear collection (MNC) program will be utilized on the Terumo BCT Spectra Optia® device so that mostly white blood cells are removed, with just a small number of platelets and red blood cells found in the final collection product. The rest of the cells and plasma in most instances will be returned to the patient. However, plasma may be collected in addition to MNC collection during the CMNC procedure if experimental design or biospecimen sourcing require additional plasma. In such cases, a small volume of approximately 20-300mLs of plasma may be collected during a single leukapheresis CMNC collection procedure. The allowed maximum of 15% of TBV of plasma may be collected at a given timepoint, which in an average adult constitutes a collection volume of approximately 700mLs. Therefore, no more than 15% of TBV may be collected during one leukapheresis procedure, occurring no more than once in a 4-week time period. Plasma may be collected for prophylactic and therapeutic monoclonal antibody discovery/development against SARS-CoV-2, or to bring the PBMC volume in a leukapheresis product to its desired cellular concentration.

At this time, *BioCytics'* use of biospecimens for its internal research efforts or as a Biobank, is strictly for non-clinical RUO (Research Use Only) and not for clinical or allogeneic recipient use. Therefore, the recommendations from the FDA regarding blood banking establishments and required donor screening labs for transmissible blood borne pathogens, HLA matching, ABO typing, and donor history questionnaires and accompanying materials (refer to Appendix 10.6) will not be utilized at the study site(s) and has been removed from other aspects of this protocol. In the event that the intent of the biobank, and subsequent use of blood and tissue products being sourced, is changed to incorporate clinical/cGMP/recipient use, this protocol will be amended and submitted for IRB review, abiding by FDA guidance for all donor related necessary procedures to comply with clinical grade cGMP products/use.

3.2.10. Microaggregate Filter for CTC Collection During Leukapheresis

Modern transfusion medicine and hemoperfusion practices utilize filtration methods to remove unwanted cells or microaggregate debris. Examples include the historical use of leukocyte depletion filters (LDFs) and modified leukocyte depletion filters (mLDFs) used for blood transfusions to remove donor WBCs to prevent recipient alloreactivity or transfusion reactions. Another example is micro-aggregate filtration during intra-operative autologous blood salvage to remove harmful blood component microaggregates (e.g., fibrin clots) and non-blood component particulate matter (e.g., fat emboli).

Version Date: 8-Dec-2020

It was historically reported that that the use of autologous non-filtered intra-operative salvaged blood may contribute to the risk of recurrence, mortality and shorter survival time in patients with malignancies. However, recent publications have been able to demonstrate the effectiveness of utilizing microaggregate filters for the removal of tumor cells during cell salvage intra-operatively in onco-surgery. 45,46

Additional studies have demonstrated that these microaggregate LDF and mLDF blood filters have been successful in minimizing adverse effects of autologous banked blood use in oncosurgery. They have been studied, designed and utilized based on the FDA approved predicate models such as: Heamonetics® SQ40™ (a microaggregate blood transfusion filter for intraoperative blood salvage) and Leukogard LG-6, Pall® (a leukocyte reduction arterial blood filter). The latter was the first clinical attempt utilizing a leukocyte depletion filter during oncologic surgery that successfully demonstrated patients tolerating the application of the system without problems during operative and postoperative follow-up. ^{48,49}

[figure not shown]
As is well known, circulating tumor cells (CTCs) are generated when individual, or groups of cells, detach from the solid tumor, whether primary or metastatic, and enter the peripheral circulation. Although CTC's are rare in peripheral blood, their presence indicates a systemic disease stage and detection of CTC's in peripheral blood have been useful in estimating prognosis and disease progression in breast, prostate, skin and colon malignancies.⁵⁰ Due to the clear prognostic and diagnostic value of CTCs for cancer patients of all stages, *BioCytics* hypothesizes that they may be depleted with 40µm microaggregate blood filters such as those utilized in intraoperative blood salvage to remove harmful microaggregates and non-blood particulate matter.⁵¹ By connecting the filters during the leukapheresis procedure where approximately 1 total blood volume is circulated through the Terumo BCT Spectra Optia® apheresis CMNC procedure, there is an increased possibility of isolating CTCs or CTC clusters within the microaggregate blood filters. Therefore, this study proposes to incorporate the use of an FDA approved 40µm microaggregate blood filter (e.g., Heamonetics® SQ40™ microaggregate high blood flow filter) to be connected downstream of the leukapheresis procedure for CTC isolation.

The use of the aforementioned SQ40™ μm filter, or other similar FDA approved filters ranging from 40μm, provide a very low residual volume which minimizes red blood cell loss and its high filtering flow rate capacity allows a reduction in the number of administration sets. ^{51,52} Thus, this may allow the filter to be placed in series or in parallel, utilizing a range of approximately 1 to 4 filters per leukapheresis collection procedure. *BioCytics* proposes that leukapheresis filtration of harmful microaggregates such as CTCs and CTC clusters, may allow further research into potential benefit by calculating pre & post leukapheresis CTC reductions from cancer patients' whole blood. In addition, the placement of these FDA approved microaggregate blood filter(s) will not adulterate the CMNC program nor IDL kit of the Terumo BCT Spectra Optia® apheresis machine as these will be placed under aseptic technique on the return IV of the cancer patient and follow *BioCytics* strict SOPs. Our goal is to obtain the most leukocytes from the counter-centrifugation cell density layering by the Spectra Optia device into the leukapheresis product; and to

Version Date: 8-Dec-2020

simultaneously obtain the most CTCs from the 40 micron in-line filter at the return IV of the patient. We also plan to compare pre & post CTC counts before and after leukapheresis to determine the CTCs in the patient, leukapheresis product, and on the filter.

Based on 40 micron screen filter size, leukopenia is not anticipated post leukapheresis collection with the utilization of microaggregate blood filter(s) in the return IV of the patient. Lymphocytes range from 8-12μm, while CTC's range from 15-40μm and CTC clusters range from 40-100 μm. Lastly, *BioCytics* internal SOP requires that all patients undergoing leukapheresis collection be closely monitored by the Principal Investigator and/or treating oncologist, including complete blood counts pre and post leukapheresis collection. To date, of the 106 successful unfiltered leukapheresis collection procedures done at Carolina BioOncology Institute, there have not been any cases of a clinically significant reduction in leukocytes post leukapheresis collection among all patient cohorts, furthering *BioCytics* belief that the use of these FDA approved in-line microaggregate blood filters will not cause clinically significant leukopenia. Reference diagram below. S4

3.2.11. Long Term Follow-Up Period

Upon completion of enrollment/screening visits and study visits, the patient will have completed the active phase of the protocol. Thereafter, the patient will enter a long term follow up period whereby survival data, tumor status, and concomitant adjuvant therapy in cancer patients may be followed through communication with the study center for an additional 5 years, as deemed appropriate by the Principal Investigator. Healthy volunteers will not be followed long-term upon study completion unless deemed appropriate by the Principal Investigator or treating physician.

3.2.12. Study Completion, Follow-up, and Close Out

Upon completion of enrollment visits for approximately 1500 patients enrolled in this observational prospective biospecimen collection laboratory study, the study will close to accrual and all active patient study visits will end, unless the study population is augmented per the

Version Date: 8-Dec-2020

Principal Investigator's discretion and formal approval of the study-specific IRB is obtained. Upon completion of the 5 year follow up period for all 1500 patients, the study will be completed and undergo formal close out.

3.2.13. Subject Withdrawal

Patients and/or healthy volunteers may be removed from study for any of the following reasons and at any time point:

- Patient choice to withdrawal consent
- Patient decline in performance status: ECOG ≥ 3
- Patient transition to home hospice and/or be unable or unwilling to return to clinic due to tumor progression
- Patient death
- At the discretion of the treating oncologist or Principal Investigator that the patient's condition or quality of life is adversely affected by repeated phlebotomy or other study procedures related to this study
- The scope of a study amendment no longer includes participation of study subject, (i.e., pediatric COVID-19 subjects)

3.2.14 Possible Toxicities

Possible toxicities or side-effects, as they relate to this observational biospecimen collection study will depend on the procedure(s) taking place. Among the most common are side-effects associated with blood draws, apheresis and biopsies/tumor resection. These are itemized below and must be disclosed by the study staff at the time of the informed consent procedure.

Possible side-effects or toxicities related to monthly blood draws may include:

- Symptomatic anemia from phlebotomy blood loss (rare)
- Discomfort at the site of blood draw such as redness, bruise, swelling (common)
- Venipuncture risk of superficial thrombophlebitis (rare)
- Port infection if drawn from central line access (rare)

Side effects from apheresis were reported in two large studies totaling 47,856 subjects.^{55,56} No life threatening, serious, or long-term problems were reported. Possible, although rare, risks and discomforts include the following:

Mild (Occurred in less than 1.3% of procedures):

- Access problems
- Hypotension
- Tingling
- Device Problems
- Urticaria
- Nausea/Vomiting
- Hematoma at puncture site

Version Date: 8-Dec-2020

Confidential 34 | Page

- Hypertension
- Flush
- Phlebitis
- Shivering, fever
- Arrhythmia
- Back Pain
- Vertigo

Severe (Rare, occurred in less than 0.11% of procedures):

- Hypotension, syncope
- Urticaria
- Fever, chills
- Nausea, vomiting
- Access Problem
- Flush
- Tingling, stitching,
- Arrhythmia

Extremely rare events (occurred in less than 0.01% of procedures):

- Bronchospasm
- Technical problem, wrong plasma
- · Abdominal pain, gastrointestinal bleeding
- Back pain, spasm
- Epilepsy
- Hypertension, asystole, chest pain
- Anaphylaxis, adverse event to drug
- Anxiety, hyperventilation

Common risks which eligible leukapheresis subjects should be informed of include the following:

- Most people feel tired. Patients should plan on little or no activity for the next 12 hours.
- Patients might have dizziness, fainting, and nausea. The risk of dizziness or fainting was lower during leukapheresis than in many studies of whole blood donation.
- Leukapheresis may temporarily lower patient platelet count. Therefore, patients should avoid activities that would put them at risk for bruising or bleeding.
- Patients may bruise more easily during the next couple of days.
- Leukapheresis may temporarily lower patient white blood cell count. Therefore, patient(s) should notify their doctor if they develop any signs of infection such as a fever.
- Patients might develop redness or pain where the needle was. They should be instructed to call the study doctor/study staff if this happens.
- Patients should be instructed to drink plenty of fluids.
- If patients get dizzy, they should be instructed to lie down with their feet elevated above their head if possible.

Version Date: 8-Dec-2020

Confidential 35 | Page

• For the next 5 hours, patient(s) should leave their bandages on and keep them dry. Patients should not do any heavy lifting or exercise during this time.

The risk of a biopsy is dependent upon where the tumor is located in a patient's body and the type of procedure it is, core needle biopsies versus surgical resection of a tumor. It is possible that the research biopsy or procedures may involve risks to patients that are not currently known or foreseeable. The treating oncologist or principal investigator will discuss additional personal risk as it relates to a biopsy procedure or surgical resection in detail. Patients may need to sign additional consent documents required by the local hospital where the biopsy or surgery is taking place.

Risks of core needle biopsies include the following:

Common - Expected to occur in 10%-25% of people:

- pain from the procedure
- bruising and soreness at the site of biopsy
- scarring at the site of biopsy
- radiation risks as mentioned above if the biopsy is done in combination with a CT scan

Rare - Expected to occur in less than 1% of people:

- infection
- internal bleeding

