4. ADVERSE EVENT REPORTING

Since this is an observational prospective biospecimen collection laboratory study, adverse events are not anticipated. Although not anticipated, any adverse event (AE) or serious adverse event (SAE) whether attributed or related to study procedures occurring in a patient after providing informed consent, will be documented in the study site(s)' electronic medical records (EMR), as well as tracked in *BioCytics*' data logs. AEs and SAEs are reviewed by the Principal Investigator, as well as by the Quality Systems Manager and QA study team members during the monthly QA meetings.

All SAEs and AEs will be assessed by the Principal Investigator or treating oncologist for severity, relationship to the investigational/study procedure(s) and whether the event meets criteria of an SAE. If criteria are met for a serious adverse event, whether attributable or related to study procedures, the SAE will be reported by the Principal Investigator to *BioCytics* immediately, and no later than 24 hours of learning of its occurrence. *BioCytics* may also contact the Principal Investigator to obtain further information on a reported Serious Adverse Event. *BioCytics* may also report the SAE to its respective Institutional Review Board immediately, and no later than 24 hours of learning of its occurrence and document all said communication/correspondence between all parties: investigator, sponsor, and IRB/IEC.

To date, *BioCytics* has observed one unexpected and unrelated death the day after a blood donation. Upon the Principal Investigator's knowledge of this event, the IRB was immediately notified, and documentation of this event was entered in the site's EMR. With respect to leukapheresis, to date there have been 135 leukapheresis collection procedures, out of which there have been only 14 mild reactions reported, constituting 10.37% of the total runs. These AE's were assessed by the clinical staff and most were due to transient mild symptoms of citrate related hypocalcemia, manifested as a mild peripheral sensory paresthesia (tingling) in toes and peri-orally, which resolved by giving an additional oral calcium carbonate (Tums) and reducing the pheresis flow rate. Other mild AE symptoms related to leukapheresis were mild chills (or

Version Date: 8-Dec-2020

Confidential 37 | Page

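### Section 3.2.14, which must be disclosed at consent, says no serious apheresis events were reported yet lists asystole and anaphylaxis, and rates mild tingling as rare (under 1.3%) although Section 4 records 14 mild reactions, mostly tingling, in 135 procedures

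*Protocol*

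**What the plan says.** Protocol Section 3.2.14 covers the side effects of blood draws, apheresis and biopsies, and makes the list binding on staff: "These are itemized below and must be disclosed by the study staff at the time of the informed consent procedure".

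The apheresis part rests on outside data: "Side effects from apheresis were reported in two large studies totaling 47,856 subjects". It then says that no life-threatening, serious or lasting problem was seen in those studies, and introduces its list with "Possible, although rare, risks and discomforts include the following". Three tiers follow:

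- "Mild (Occurred in less than 1.3% of procedures": 14 entries, one of which is tingling.
- "Severe (Rare, occurred in less than 0.11% of procedures": 8 entries, one of which again includes tingling.
- Extremely rare, under 0.01% of procedures: the entries include asystole and anaphylaxis.

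After the tiers comes a separate list of common leukapheresis risks, without frequencies. It covers tiredness, dizziness, fainting, nausea, lower platelet and white cell counts, bruising and needle-site redness or pain. Neither tingling nor any citrate reaction is in it.

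Section 4 gives this study's own record. In 135 leukapheresis procedures, "there have been only 14 mild reactions reported, constituting 10.37% of the total runs". Of these, "most were due to transient mild symptoms of citrate related hypocalcemia", "manifested as a mild peripheral sensory paresthesia (tingling) in toes and peri-orally". The others were chills and hunger attributed to mild hypoglycemia. Section 3.2.14 neither repeats this rate nor refers to it.

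**The concern.** The two halves of the point differ in kind.

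The first is a contradiction inside one section. Staff would state that no serious event was reported and then read out asystole and anaphylaxis as events that occurred.

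The second is a disclosure list that has not been brought into line with the sponsor's own data. The outside rate for mild tingling is given under a rare label, while another section of the same protocol shows tingling to be the usual reaction at this site.

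At stake is the accuracy of risk information for patients and for healthy volunteers, who gain nothing clinically from the procedure and may repeat it every 4 weeks. No endpoint or analysis is affected.

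**Working it through.** **1. The seriousness statement (Section 3.2.14).** The section says that no life-threatening or serious problem was reported. The lowest tier, for which no other source is named, lists asystole and anaphylaxis among events that occurred. An event that occurred was seen at least once. For scale, if each of the 47,856 subjects had one procedure (an assumption, since the number of procedures is not given), the tier's ceiling is 0.0001 × 47,856 = 4.8 events. That is a small number, but it is not zero. No calculation is needed to see that the two statements conflict.

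**2. The study's own rate (Section 4).** Inputs are 14 mild reactions and 135 procedures.

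- 14/135 = 0.1037, which reproduces the protocol's 10.37%.
- The exact (Clopper-Pearson) 95% interval is the 2.5% quantile of Beta(14, 122) to the 97.5% quantile of Beta(15, 121), which gives 5.8% to 16.8%.
- This treats the 14 reactions as falling in 14 separate, independent runs, as the protocol's own percentage implies.

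**3. What the 1.3% can be compared with.** Section 3.2.14 does not say whether the figure covers all mild events together or each listed item.

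- *Overall rate:* 135 × 0.013 = 1.8 reactions expected against 14 seen. The ratio is 0.1037/0.013 = 8.0, and the chance of 14 or more at a true 1.3% is 3.4 × 10⁻⁹.
- *Ceiling per item:* the 14 mild entries could sum to 14 × 1.3% = 18.2%. At 18.2%, the chance of 14 or more in 135 is 0.996, so 10.4% would be no surprise. Only tingling can then be compared.

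**4. Tingling alone.** Section 4 gives no count. I take most of 14 as at least 8 (assumption).

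- 8/135 = 5.9%, exact 95% CI 2.6% to 11.3%.
- Ratio to the ceiling: 0.0593/0.013 = 4.6.
- The chance of 8 or more at a true 1.3% is 0.0004.
- If chills and hunger account for one reaction each, at most 12 are tingling: 12/135 = 8.9% (CI 4.7% to 15.0%), or 6.8 times the ceiling.

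**5. Repeat donors.** Reactions may cluster within a donor, and the number of donors is not given. Dividing both count and denominator by a design effect *d* in the beta quantiles, the lower limit for 8 tingling events falls to 1.3% at *d* of about 2.55. The point estimates do not change.

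**6. The word rare.** In its biopsy text the same section uses common for 10% to 25% and rare for under 1%. That scale was set for biopsies, but by it tingling at 5.9% or more is not rare.

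**The case against.** The strongest reply is that the frequency half is not a contradiction. Section 3.2.14 attributes its rates to outside studies in the past tense, Section 4 reports local experience openly, and both can be true. That stands: the outside figure may be right for its source. What remains is that the list staff must disclose carries only the outside rate, and the local one is higher.

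Four stronger readings are tempting and are not supported:

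- *That the section calls every apheresis effect rare.* It does not. The list of common risks follows, and it includes dizziness and nausea. The point is confined to mild tingling, which that list omits.
- *That 1.3% is the only tingling frequency given.* Tingling also stands in the severe tier, at under 0.11%. The 1.3% is the figure for mild tingling.
- *That the study's reaction rate is simply eight times the disclosed one.* This holds only if 1.3% is an overall rate, which the text leaves open.
- *That participants were misinformed.* Section 7.3 requires risks and discomforts to be explained through the consent form, which is not shown. It may repeat these figures or may add the local rate.

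It may also be said that severe is not the same as serious. That is correct, but the contradiction rests on asystole and anaphylaxis, not on the severe tier. Finally, the hunger symptoms are trivial and the list does not claim to be complete, so their absence is not a defect.

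**Conclusion.** The point holds on both halves, with different certainty.

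The seriousness statement and the asystole and anaphylaxis entries contradict each other on the face of Section 3.2.14. This rests on no assumption.

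Mild tingling is presented as rare, at under 1.3%, while this study's record shows 14 mild reactions in 135 procedures, most of them tingling. With at least 8 of the 14 taken as tingling, the local rate is 5.9% or more, about 4.6 times the ceiling. The lower limit of 2.6% assumes independent runs, and strong clustering by donor could bring it down to 1.3%. The comparison for tingling holds whether 1.3% is overall or per item; the eightfold comparison for all mild reactions holds only in the first case.

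This should be fixed. It concerns the protocol's mandated disclosure list and does not show what participants were actually told.

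**What to change.** Revise Section 3.2.14, and the consent text if it repeats these figures:

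- Reconcile the statement about life-threatening and serious problems with the asystole and anaphylaxis entries.
- State this study's own rate, 14/135 (10.4%, mostly tingling), beside the outside rate, and say whether 1.3% is an overall rate or applies to each symptom.
- Stop presenting mild tingling as rare.

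Listing the mild hypoglycemia symptoms from Section 4 is optional.

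The cost is wording in one section, possibly in the consent form, and a less favourable stated risk. No procedure, endpoint or analysis changes.
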